## 5.4. Subjects Lost to Follow-up

If a subject fails to return for the 90-day follow-up visit, five (5) calls to their last known contact number will be done within two (2) weeks. If those attempts are unsuccessful, a certified letter will be sent to their most current mailing address, reminding them of their study obligations. When all reasonable attempts to locate the subject have been exhausted, including contacting the subject's general practitioner and additional documented contacts (e.g., family members or trusted individuals), the subject will be considered lost to follow-up. Documentation is required for all attempts to locate the subject.

The primary method for analysis will use multiple imputation to address missing data. As a sensitivity analysis for the primary endpoint, the baseline value will be imputed for the 90-day result, functionally resulting in no change from baseline in the mRS score. A separate sensitivity analysis will be conducted imputing the worst mRS score at 90-days recorded for a patient within their respective treatment group. A sensitivity analysis of the primary safety endpoint will also be conducted. Additional details are provided in Section 8 of this protocol and the SAP.

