Indications for Use	
Study Reports summarizing data from this investigation will be submitted to the FDA as part of an IDE application seeking the following indications for use:
 
 
1. The Envi™-SR is indicated for use to restore blood flow in the neurovasculature by removing thrombus for the treatment of acute ischemic stroke to reduce disability in patients with a persistent, proximal anterior circulation, large vessel occlusion, and smaller core infarcts who have first received intravenous tissue plasminogen activator (IV t-PA). Endovascular therapy with the device should be started within 6 hours of symptom onset.
 
2. The Envi™-SR is intended to restore blood flow in the neurovasculature by removing thrombus in patients experiencing ischemic stroke within 8 hours of symptom onset. Patients who are ineligible for IV t-PA or who fail IV t-PA therapy are candidates for treatment.
 
3. The Envi™-SR is indicated for use to restore blood flow in the neurovasculature by removing thrombus for the treatment of acute ischemic stroke to reduce disability in patients with a persistent, proximal anterior circulation, large vessel occlusion of the internal carotid artery (ICA) or middle cerebral artery (MCA)-M1 segments with smaller core infarcts (0-50 cc for age < 80 years, 0-20 cc for age ≥ 80 years). Endovascular therapy with the device should start within 6-24 hours of time last seen well in patients who are ineligible for intravenous tissue plasminogen activator (IV t-PA) or who fail IV t-PA therapy.
 

Device Description	The Envi™-SR is a self-expanding, nitinol stent-like mechanical thrombectomy device that is designed to be delivered to the neurovasculature through a microcatheter to retrieve thrombus.
Duration of Study	The total duration of the study is expected to be approximately 36-48 months
Duration of Subject Participation	Subjects will be in study for up to 90 days (± 15 days).
Primary Effectiveness Endpoint	The proportion of subjects with good clinical outcome defined as Modified Rankin Score (mRS) of ≤2 as assessed by a blinded assessor at 90 days (± 15 days).
Primary Safety Endpoint	Device-related or procedure-related symptomatic intracranial hemorrhage (sICH) defined by the Heidelberg Bleeding Classification at 24 hours (-8/+12 hours) (as read by the Core Lab and adjudicated by Clinical Events Committee (CEC)).

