Exclusion Criteria	
 
1. Life expectancy likely less than six (6) months.
 
2. Females who are pregnant or breastfeeding.
 
3. Known history of severe allergy (more than rash) to contrast medium that cannot be medically controlled.
 
4. Suspicion of renal failure (Renal failure as defined by a serum creatinine >3.0 mg/dL (264 µmol/L) or Glomerular Filtration Rate (eGFR) <30).
 
5. Severe, sustained hypertension (Systolic Blood Pressure >185 mmHg or Diastolic Blood Pressure >110 mmHg) NOTE: If the blood pressure can be successfully reduced and maintained at the acceptable level using medication the subject can be enrolled.
 
6. Currently participating in another interventional (drug, device, etc.) research project that may confound the results of this study.
 
7. Known hereditary or acquired hemorrhagic diathesis, coagulation factor deficiency. (A subject without history or suspicion of coagulopathy does not require INR or prothrombin time lab results to be available prior to enrollment.)
 
8. Known history of platelet count <100,000/µL.
 
9. Baseline blood glucose of <50mg/dL (2.78 mmol) or >400mg/dL (22.20 mmol).
 
10. Subjects with occlusions in multiple vascular territories (e.g., bilateral anterior circulation, or anterior/posterior circulation).
 
11. CT or MR evidence of hemorrhage.
 
12. Seizures at stroke onset.
 
13. Suspicion of aortic dissection.
 
14. Patients with known hypersensitivity to nickel-titanium.
 
15. Evidence of dissection in the extra or intracranial cerebral arteries.
 
16. Stenosis, or any occlusion, in a proximal vessel that requires treatment or prevents access to the site of occlusion.
 
17. Presumed septic embolus, suspicion of bacterial endocarditis, or other serious infection.
 
18. Suspected cerebral vasculitis based on medical history and CTA/Magnetic Resonance Angiogram (MRA).
 
19. Excessive vascular access tortuosity that will likely prevent endovascular access.
 
20. Baseline CT or Magnetic Resonance Imaging (MRI) showing intracranial tumor (except asymptomatic small meningiomas less than three (3) cm).
 
21. Significant mass effect with midline shift
 
22. Treatment with any cleared thrombectomy devices or other intra-arterial (neurovascular) therapies three months prior to use of treatment device
 
23. Unlikely to be available for 90-day (± 15 days) follow-up (e.g. no fixed home address, visitor from overseas).
 
24. Rapid neurological improvement prior to study enrollment suggesting resolution of signs/symptoms of stroke such as a decrease that leads to an NIHSS below the study cut-off of six (6).
 
25. Patient has suffered a hemorrhagic or ischemic stroke or TIA in at least the last three (3) months.
 
26. Patients with a pre-existing neurological or psychiatric disease that would confound the neurological or functional evaluations, mRS score at baseline must be ≤ 2. This excludes patients who are severely demented, require constant assistance in a nursing home type setting or who live at home but are not fully independent in activities of daily living (toileting, dressing, eating, cooking and preparing meals, etc.).
 
27. Known cancer with metastases.
 
28. Subject currently uses or has a recent history of illicit drug(s), which includes marijuana.
 
29. Recent past history (within three (3) months) or clinical presentation of intracranial hemorrhage (ICH), subarachnoid hemorrhage (SAH), ruptured arteriovenous malformation (AVM) or ruptured aneurysm.
 

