## 6.5. Inclusion Criteria

Study subjects must meet ALL of the inclusion criteria listed below:

- 1) Clinical signs consistent with acute ischemic stroke
- 2) Pre-stroke Modified Rankin Score  $\leq 2$
- 3) Age 18 years and no upper limit (patient must be 18 years old at time of consent.)
- 4) NIHSS  $\geq 6$  at the time of randomization
- 5) Subject is able to start treatment (defined as time of arterial puncture) within 24 hours of stroke onset or last known well and within 90 minutes from last baseline CT/ MRI.
- 6) Imaging: For strokes in the anterior circulation the following imaging criteria should also be met:
  - a) If stroke onset (as defined by the time the patient was last seen at baseline) is within 6 hours: Baseline ASPECTS  $\geq 6$  on non-contrast CT (NCCT) or DWI-MRI;
  - b) If stroke onset is within 6-24 hours, advanced imaging with either CT perfusion or DWI-MRI is required. Baseline infarct volume must be  $\leq 50$ cc for patients under 80 years old and  $\leq 20$ cc for patients 80 years or older.
- 7) Location: Angiographic confirmation of an occlusion of an ICA (including T or L occlusions), M1 or M2 MCA with eTICI flow of zero (0) – one (1).
- 8) Patients for whom IV t-PA is indicated, are treated with IV t-PA without delay.
- 9) IV t-PA, if used, is initiated within three (3) hours of stroke onset (onset time is defined as the last time when the patient was witnessed to be at baseline), with investigator verification that the subject has received/is receiving the correct IV t-PA dose for the estimated weight.
- 10) Consent: The patient or the patient's LAR has signed and dated an Informed Consent Form.
- 11) Will comply with protocol follow-up schedule.
- 12) Patient was ambulatory prior to stroke, i.e. able to walk without another person's assistance.

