#### **6.8.2.3. Neurologic Evaluation**

Screening NIHSS should be recorded as performed. At screening, a pre-stroke mRS will be obtained from the subject or the subject's caretaker.

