## 6.8.10. Schedule of Events Summary Table

Study Requirement	Screening	Procedure	Post Procedure				
	Within 24 hrs. of stroke onset	Time 0	24 Hours (-8/+12)	7 Day (-2/+3) or Discharge 	30 Day (±14) 	90 Day (±15) 	Unscheduled
Informed consent	X 						
Pregnancy test	X 						
NIHSS Score	X		X 	X 			
Modified Rankin Scale (mRS)	X 				X	X 	X
Medical history	X						
Physical examination	X			X 			
Blood Pressure and Pulse	X						
Assess/confirm study eligibility	X						
Cerebral Imaging (CT or MRI)	X 		X 				
Hemoglobin and Platelet Count	X 						
Serum Glucose	X 						
Serum Creatinine or eGFR	X 						
INR, aPTT	X 						
Angiography	X 	X 					
Randomization		X					
Mechanical thrombectomy		X					
Concomitant medications	X			X	X	X	X
Record adverse events 	X	X	X	X	X	X	X

(1) Patient or Legally Authorized Representative must sign informed consent prior to screening specific tests which are beyond the local standard of care.

(2) Per institutional standard of care, for females of childbearing potential, subjects must have a documented negative pregnancy test prior to device insertion except in the case of local regulations and ethic committee approvals requiring consent post the emergency situation.

(3) Pre-ictus (Latin for Stroke)

(4) Record all adverse events from the time of signature of the ICF.

(5) To be performed at 7 days (-2/+3 days) or at discharge (whichever occurs first).

(6) Perform baseline to verify the angiographic inclusion/exclusion criteria are met.

(7) Perform angiography after every device pass, and after each additional therapy device pass. Obtain a final angiogram at the end of the interventional procedure.

(8) Assessed by blinded and certified study team member, mRS per the RFA-A.

(9) Visit may be conducted by telemedicine if clinical visit not possible.

(10) Physical exam to be conducted per institution standard of care

(11) If required per local standard of care or inclusion/exclusion criteria

(12) Per institutional standard of care. MRI with DWI is preferred, CT is acceptable. It is preferred that the same imaging modality is used at 24 hour timepoint as at baseline (CT or MRI) to make direct comparison easier.

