### Maximum Sample Size

If the gap narrows between the 2 randomized groups to 49.5% (Control) and 50.5% (Envi™-SR), 426 total patients (ITT) will be required (type 1 error rate of 2.5%, power of 80%). A loss to follow-up rate of 5% or less is expected. Missing data will be imputed as described in section 8.2.2. As multiple imputation could dampen the signal from the subject data that is imputed, an additional 5% of subjects may be added to compensate for any potential impact, leading to a total sample size of 448 subjects (ITT).

All estimates are performed based on the ITT population. However, all enrolled subjects (i.e., consented), including enrolled screen failures, will count toward the maximum sample size of 560 patients. The rate of enrolled screen failures is not expected to exceed 25%. Therefore, the maximum sample size for enrollment will be the ITT maximum sample size plus 25%, or 560 patients.

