Method 2: mRS based on the observed results for patients where additional therapies were not used to retrieve the clot. Subjects who required additional therapy for reperfusion failure or additional off-label therapies to retrieve the clot will be automatically treated as primary effectiveness endpoint failures. Multiple imputation will be used to impute the mRS score for patients who become lost to follow-up prior to the 90 day evaluation.

Method 3: mRS based on the observed results for patients where additional therapies were not used to retrieve the clot. Subjects who required any additional therapy to retrieve the clot will be automatically treated as primary effectiveness endpoint failures. Multiple imputation will be used to impute the mRS score for patients who become lost to follow-up prior to the 90 day evaluation.

An important consideration in requiring any patient who received additional therapy to retrieve the clot is acknowledging this is truly a random effect. The observed mRS at 90 days could indicate no difference in functional independence between the 2 randomized treatment groups, but the use of additional therapies could, by chance and chance alone, result in non-inferiority being achieved or lost. For this reason, Method 1 is the primary method for the derivation of the primary effectiveness endpoint for the study; Method 2 and Method 3 represent secondary derivations of the primary effectiveness endpoint.

Two (2) additional sensitivity analyses will be prepared to explore alternative methods for imputation for patients who are lost to follow-up (ref. Section 5.4) for the primary endpoint. The first sensitivity analysis will impute the baseline value for the 90-day result, functionally resulting in no change from baseline. The second sensitivity analysis will be conducted imputing the worst score at 90-days recorded for a patient within their respective treatment group for patients who are lost to follow-up. Additional details are provided in the SAP.

Additionally, as a final sensitivity analysis of the primary endpoint, a logistic model will be performed within the imputed datasets derived using multiple imputation. This model will incorporate the stratification variables specified in the randomization as covariates and with randomization group assignment. Under the guise of a sensitivity analysis, separate sub-group analysis will be prepared to examine factors that may have influenced the 90-day mRS scores.

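### The baseline-value sensitivity analysis counts every eligible lost subject as a success, because baseline mRS is the pre-stroke score; it is a best case and should be labelled or replaced

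*Combined protocol and SAP*

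**What the plan says.** Section 5.4 states that, as a sensitivity analysis of the primary endpoint, "the baseline value will be imputed for the 90-day result, functionally resulting in no change from baseline in the mRS score". Section 8.3.1 repeats it: "The first sensitivity analysis will impute the baseline value for the 90-day result, functionally resulting in no change from baseline". Both sections pair it with a second analysis that gives a lost subject the worst 90-day score recorded in the subject's own arm. Section 8.2.2 adds carry-forward of the last post-procedure observation and a tipping-point analysis, the latter in one sentence without detail.

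Section 6.8.2.3 says what the baseline score is: "At screening, a pre-stroke mRS will be obtained from the subject" or a caretaker. The schedule of events (6.8.10) footnotes the screening mRS as pre-ictus, and the next scheduled mRS is at day 30. Inclusion criterion 2 caps the "Pre-stroke Modified Rankin Score" at 2, and exclusion criterion 26 uses the word baseline for the same limit: "mRS score at baseline must be ≤ 2". The synopsis defines the primary endpoint as "The proportion of subjects with good clinical outcome defined as Modified Rankin Score (mRS) of ≤2 as assessed by a blinded assessor" at 90 days.

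**The concern.** No change from baseline usually suggests a cautious imputation, in which the subject has gained nothing from treatment. That holds when baseline is measured after disease onset. Here baseline precedes the stroke, so no change means full return to pre-stroke function after a stroke with NIHSS of at least 6. For that subject no imputed value could be more favourable on the binary endpoint.

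A sensitivity analysis in a non-inferiority trial should put the conclusion under stress. This one shrinks a true deficit when loss is balanced, and credits Envi-SR with extra successes when Envi-SR loses more subjects. A reader who takes the description at face value could count agreement between this analysis and the primary result as evidence of robustness that it does not provide.

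**Working it through.** **Step 1: definitions.** An eligible subject's baseline mRS is 0, 1 or 2. The rule copies it to day 90. Success is 90-day mRS of 2 or less. So every eligible lost subject is a success, against planned rates of 46% (Control) and 50.5% (Envi-SR) for all subjects. At the 5% planning ceiling for loss this concerns about 0.05 × 270 = 13.5 (14) subjects, or 0.05 × 448 = 22.4 (22).

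**Step 2: reproduce the plan's sample size.** Inputs from 8.2: 46%, 50.5%, margin 12.5 points, one-sided 2.5%. Power of 80% is stated for the 426 figure and assumed here for 270 as well. With unpooled variance,

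n per arm = (1.960 + 0.842)² × (0.46×0.54 + 0.505×0.495) / (0.125 + 0.045)² = 7.849 × 0.4984 / 0.0289 = 135.4, so 136 per arm or 272 in total, against 270 stated. The inputs are being read correctly.

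**Step 3: effect of the rule.** With true rate p and share lost l, the rate after imputation is (1 − l)p + l. This assumes that lost subjects would have had the same success rate as those retained. Two consequences follow:
- With equal loss l, the difference is multiplied by (1 − l).
- With equal true rates p, a spurious difference of (l_Envi − l_Control)(1 − p) appears. At p = 46%, each extra point of Envi-SR loss adds 0.54 points.

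**Step 4: true deficit at the margin.** Envi-SR 33.5%, Control 46%. The chance that this analysis meets the margin is Φ[(D + 0.125)/SE − 1.96], where D is the difference after imputation and SE is the unpooled standard error. Only the 5% figure comes from the plan ("A loss to follow-up rate of 5% or less is expected"); the unequal splits are assumptions, chosen to average 5%.

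| Loss Envi-SR / Control | Envi-SR after | Control after | D (points) | Chance, 135 per arm | Chance, 224 per arm |
|---|---|---|---|---|---|
| 0% / 0% | 33.5% | 46.0% | -12.5 | 2.5% | 2.5% |
| 5% / 5% | 36.8% | 48.7% | -11.9 | 3.2% | 3.4% |
| 6% / 4% | 37.5% | 48.2% | -10.7 | 4.9% | 5.9% |
| 8% / 2% | 38.8% | 47.1% | -8.3 | 10.5% | 14.7% |

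Example, 8%/2%: 0.335×0.92 + 0.08 = 0.3882; 0.46×0.98 + 0.02 = 0.4708; D = -0.0826; SE at 135 per arm = 0.0600; (-0.0826 + 0.125)/0.0600 − 1.96 = -1.25, which gives 10.5%.

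**Step 5: the paired worst-score analysis.** mRS 6 is death, and 8.2 plans on 90-day mortality of about 13.8%, or about 0.138 × 135 = 19 deaths per arm. The worst recorded score will almost certainly be 6 in both arms, so all lost subjects become failures. At 8%/2% this gives 0.335×0.92 − 0.46×0.98 = -14.3 points. At 5%/5% it gives 0.335×0.95 − 0.46×0.95 = -11.9 points, the same as the best case. With balanced loss, therefore, neither of the two rules is adverse to Envi-SR.

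**The case against.** The strongest reply is that nothing is decided on this analysis. Non-inferiority rests on Method 1 with multiple imputation in the ITT population, and 8.3.1 presents the baseline-value rule only as one way to explore alternative imputations. That stands. A reader might infer from the last row of the table that the trial's type I error rises to 10% or 15%. The documents do not support that: those figures describe how often one supporting analysis meets the margin, under a loss split that appears nowhere in the plan. Subjects are blinded to arm, so a fourfold difference in loss would need its own justification.

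A reader might also infer that the missing-data plan as a whole is tilted towards Envi-SR. It is not. In the 8%/2% case the worst-score result (-14.3) would visibly disagree with the baseline-value result (-8.3), and carry-forward and tipping-point analyses are planned as well. Read together, the two rules form a best-case and worst-case pair. This also stands, but the plan does not label them so, and neither rule treats the arms asymmetrically against Envi-SR.

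Three smaller qualifications hold. A subject randomized in error with a pre-stroke mRS above 2 stays in ITT and would be imputed as a failure. Under Methods 2 and 3 the additional-therapy rule could override an imputed success. And 5.4 and 8.3.1 defer details to the SAP; the text reviewed contains no separate SAP section that redefines baseline, though one cannot be excluded.

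**Conclusion.** The point holds as a flaw in one sensitivity analysis. As defined in the protocol, it scores all eligible lost subjects as successes, while its description conveys only an absence of change. With 5% loss in each arm the distortion is small: 0.6 points at the margin, and a 3.2% instead of 2.5% chance of meeting it at 135 per arm (3.4% at 224). It grows with excess loss in the Envi-SR arm, reaching -10.7 to -8.3 points and about 5% to 10% (135 per arm) or 6% to 15% (224 per arm) over the assumed 6%/4% to 8%/2% range. These figures rest on a normal approximation, a Control rate of 46%, and lost subjects resembling retained ones. The primary analysis is unaffected. Severity is moderate: worth correcting before unblinding, because relabelling or replacing the analysis once results are known would look post hoc.

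**What to change.** In 5.4 and 8.3.1:
1. Replace the baseline-value imputation, or keep it and label it openly as the bound in which all lost subjects count as successes.
2. Add a bound adverse to Envi-SR: missing Envi-SR = failure, missing Control = success.
3. Specify that the tipping-point analysis in 8.2.2 varies the missing outcomes separately in each arm.

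The worst-score analysis can stay as it is; in effect it already supplies the bound in which all missing subjects are failures, so no separate one is needed.

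The cost is some wording and a few lines of code, with no new data. The sensitivity results will be less favourable. At the planning rates with 5% loss per arm, the added bound gives 0.505×0.95 − (0.46×0.95 + 0.05) = 0.4798 − 0.4870 = -0.7 points. With SE = √[(0.4798×0.5202 + 0.4870×0.5130)/135] = 6.08 points, the lower limit is about -12.6, just beyond the margin. It should therefore be presented as an extreme bound and read with the tipping-point result, not as a second test of non-inferiority.

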## 6. Study Design

The study is designed as a prospective, multinational, randomized, parallel group-controlled, blinded, non-inferiority study to evaluate the performance of the Envi™-SR against devices currently on the market for the same indication.

### 6.1. Allocation

Subjects who consent and meet the inclusion/exclusion criteria will be randomized to one of the following two Treatment Arms: Envi™-SR or Control Device. Subjects will be randomized 1:1 to each Treatment Arm.

#### 6.1.1. Intervention Model

Subjects will be randomized in parallel assignment.

### 6.2. Control Device

Currently there are two FDA-cleared stent retriever families with indications for treatment of acute ischemic stroke: the Stryker Neurovascular Trevo® family and the ev3 Neurovascular/Medtronic Solitaire™ family. The Trevo® family consists of the Trevo ProVue®

Retriever, Trevo® XP ProVue Retriever, and Trevo NXT™ ProVue Retriever. The Solitaire™ Revascularization Device family includes the following: Solitaire™ Platinum, Solitaire™ 2, Solitaire™ 4, and Solitaire™ X.

All Control Devices used must be used within their Indications for Use.

The proposed Envi™-SR indications for use match the Trevo® family of devices. Hence the time from stroke onset to usage (up to 24 hours) and imaging criteria are identical and the inclusion/exclusion criteria for the NV-001 study align with this indicated patient population.

The Solitaire™ Revascularization Device family has similar indications for use, however the indicated time from stroke onset to usage is up to 16 hours from onset or time last seen well (TLSW). Therefore, in the case of a subject randomized to the Control Device at 16 to 24 hours from onset or TLSW, only the Trevo® family will be permitted to be used.

The devices in Table 6.1 are currently cleared and may be used as the Control Device.

Table 6.1: Control Devices for ENVI RCT		
Family	Product	Size
Stryker Neurovascular Trevo®	Trevo ProVue® Retriever	4x20mm
	Trevo® XP ProVue Retriever	3x20mm
		4x20mm
		4x30mm
		6x25mm
ev3 Neurovascular/ Medtronic Solitaire™	Solitaire™ Platinum Revascularization Device	4x20mm
		4x40mm
		6x20mm
		6x24mm
		6x40mm
	Solitaire™ X Revascularization Device	4x20mm
		4x40mm
		6x20mm
		6x24mm
		6x40mm
	Solitaire™ 2 Revascularization Device	4x15mm
		4x20mm
		4x40mm
		6x20mm
		6x30mm

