#### **8.3.5. Evaluating the Effect of Different Control Devices**

The method to be applied for examining the effect of different control devices will facilitate the generation of adjusted estimates to contrast against the unadjusted estimates. The adjusted

estimates for the primary effectiveness and safety endpoints will introduce the effect of different control devices; the unadjusted estimates for the primary effectiveness and safety endpoints will only consider the randomized treatment assignment in the model. This sensitivity analysis will address the fundamental question relative to the effect of the different devices and is considered more informative than adding an interaction term into the model for analysis. To provide further insight into the results, the model will be run with the interaction term retained for treatment and different control devices.

To assess the effect of different control devices used in the control arm of the study, a random effects model will be used to calculate the overall estimate adjusted for each of the 2 device types (Trevor and Solitaire). The model that will be used to derive the estimates and the standard errors is presented in the SAP. From the solution for fixed effects, the exponentiation of the estimates and the standard error will provide adjusted confidence limits to assess the effect.

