### **8.3.7. Evaluating the Effect of Time Last Seen Well (0-6 hours and >6 to 24 hours)**

The method to be applied for examining the effect of time last seen well (TLSW) will facilitate the generation of adjusted estimates to contrast against the unadjusted estimates. The adjusted estimates for the primary effectiveness and safety endpoints will introduce the effect of the time last seen well (0-6 hours and >6 to 24 hours); the unadjusted estimates for the primary effectiveness and safety endpoints will only consider the randomized treatment assignment in the model. This sensitivity analysis will address the fundamental question relative to the effect of the time last seen well (0-6 hours and >6 to 24 hours) and is considered more informative than adding an interaction term into the model for analysis. To provide further insight into the results, the model will be run with the interaction term retained for treatment and time last seen well (0-6 hours and >6 to 24 hours).

To assess the effect of the time last seen well (0-6 hours and >6 to 24 hours), a random effects model will be used to calculate the overall estimate adjusted for the discrete time segments. The model that will be used to derive the estimates and the standard errors is presented in the SAP. From the solution for fixed effects, the exponentiation of the estimates and the standard error will provide adjusted confidence limits to assess the effect.

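### The control-device sensitivity analysis mixes device family with treatment time, because Control subjects at 16–24 h can only receive Trevo (minor)

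*Combined protocol and SAP*

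**What the plan says.** Section 6.2 names two Control families. For Solitaire, "the indicated time from stroke onset to usage is up to 16 hours from onset or time last seen well (TLSW"), whereas the Trevo indication runs to 24 h. Hence the rule that for a "subject randomized to the Control Device at 16 to 24 hours from onset or TLSW, only the Trevo® family will be permitted". The entry window in Section 6.5 covers the whole period: "Subject is able to start treatment (defined as time of arterial puncture) within 24 hours of stroke onset or last known well".

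Section 8.3.5 describes a sensitivity analysis of the primary effectiveness and safety endpoints by Control device. The unadjusted estimates "will only consider the randomized treatment assignment in the model". For the adjusted ones, "a random effects model will be used to calculate the overall estimate adjusted for each of the 2 device types (Trevor and Solitaire"). In addition, "the model will be run with the interaction term retained for treatment and different control devices". The section mentions neither time from onset nor a common time window, and it refers to the SAP for the model itself.

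Time is handled separately. Section 8.3.7 is headed "Evaluating the Effect of Time Last Seen Well (0-6 hours and >6 to 24 hours"), and there "a random effects model will be used to calculate the overall estimate adjusted for the discrete time segments". The randomisation factor for time is also cut at 6 h (synopsis, Statistics). One sentence of the imputation text in Section 8.2.2 uses 4 h instead.

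**The concern.** Every Control subject at 16–24 h is meant to be a Trevo subject and none a Solitaire subject. The imbalance comes from a protocol rule, so further enrolment does not remove it. Randomisation does not remove it either, because subjects are assigned to Envi-SR or Control and not to a Control family.

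The plan itself treats time as prognostic. The Introduction calls time to reperfusion critical for prognosis, time is a randomisation factor, and Section 8.3.7 is devoted to it. If outcome at 16–24 h differs from outcome before 16 h, the Trevo and Solitaire groups will differ even when the devices perform identically. Envi-SR (0–24 h) against Solitaire (0–16 h) is unlike-for-unlike in the same way. What is at stake is how a supportive analysis would be read: an apparent device difference could be a time effect, or a real one could be masked.

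**Working it through.** **The plan's own figure.** The documents give no figure for the family analysis. The nearest is the target size, which fixes the number of Controls. With 46% v 50.5%, margin 12.5 points, one-sided 2.5% and 80% power:

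n per arm = (1.960 + 0.842)² × (0.46×0.54 + 0.505×0.495) / (0.125 + 0.045)² = 7.849 × 0.4984 / 0.0289 = 135.4, rounded up to 136.

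That is 272 in total against the stated 270 (135 Controls), so the figure reproduces closely. The maximum ITT size of 448 gives 224 Controls.

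**Assumed inputs** (none is in the documents):

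- f, share of Controls at 16–24 h: 5–20%
- s, Trevo share among Controls up to 16 h: 50% (30% as a variant)
- d, drop in good outcome at 16–24 h: 5–15 points; a negative d reverses every sign below

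**Formulas**, with the two families truly equal:

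- Late share within Trevo: q = f / (f + (1 − f)s). Within Solitaire it is 0.
- Apparent Trevo − Solitaire gap: −q × d.
- Shift in Envi-SR − Solitaire: −f × d, since 1:1 randomisation gives Envi-SR about the same late share f as the whole Control arm.

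The false-signal rate below is for a two-sided 5% z-test of Trevo v Solitaire with unpooled variance and overall Control success held at 46%. The plan states no such test; the rate serves only to show scale.

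| f | d (points) | q (s = 50%) | Gap (points) | False signal, 135 Controls | False signal, 224 Controls |
|---|---|---|---|---|---|
| 5% | 5 | 0.05/0.525 = 9.5% | −0.5 | 5.0% | 5.1% |
| 10% | 10 | 0.10/0.55 = 18.2% | −1.8 | 5.5% | 5.8% |
| 20% | 10 | 0.20/0.60 = 33.3% | −3.3 | 6.7% | 7.8% |
| 20% | 15 | 33.3% | −5.0 | 8.8% | 11.4% |

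With s = 30%, f = 20% and d = 15: q = 0.20/0.44 = 45.5% and the gap is −6.8. The largest Envi-SR v Solitaire shift in the range is 0.20 × 15 = 3.0 points. If d = 0, every gap is 0.

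**Against sampling error.** Take the last row with 135 Controls. Trevo has 0.60 × 135 = 81 subjects and Solitaire 54. The early rate is 46 + 0.20 × 15 = 49%, and the Trevo rate is 49 − 5 = 44%. SE = √(0.44×0.56/81 + 0.49×0.51/54) = 8.8 points, so the 95% interval is about ±17 points around a bias of 5.

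**Does the 6 h cut help?** Only partly. Take f = 20%, s = 50%, d = 10, and assume a further 30% of Controls at 6–16 h.

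- Within the stratum at 6 h or later, the late share of Trevo is 0.20 / (0.20 + 0.30×0.50) = 57.1%, a gap of −5.7. In the earlier stratum the gap is 0.
- The Mantel–Haenszel weights are 0.25×0.25/0.50 = 0.125 (earlier) and 0.35×0.15/0.50 = 0.105 (later).
- The stratified gap is −5.7 × 0.105/0.230 = −2.6, against −3.3 unadjusted.

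A 4 h cut also leaves 16–24 h merged with earlier times.

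**After restriction to 0–16 h.** Both families are permitted throughout, so q = 0 and the rule-driven gap is 0 in every scenario. Controls remaining are 135 × 0.95 = 128 down to 135 × 0.80 = 108, or 213 down to 179 of 224.

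**The case against.** The strongest reply is that Section 8.3.5 carries little weight. It is a sensitivity analysis that sets adjusted treatment-effect estimates beside unadjusted ones. It states no stand-alone Trevo v Solitaire test, no separate Envi-SR v Solitaire contrast and no decision rule. A reader might infer that it is the evidence on which the two families are pooled. The text does not say so; for data of this kind, poolability is raised for geography (Section 6.10.1), not for Control family. This stands, and it lowers the severity.

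Second, the protocol defers the model to the SAP, and no SAP model text appears in the document reviewed. A time covariate there cannot be excluded. This also stands. To deal with the problem, such a covariate would have to use continuous time or a cut at 16 h, and with no Solitaire subject beyond 16 h any adjustment in that range would be extrapolation.

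Third, every input to the size is assumed and the sign is open. Beyond 6 h, entry requires a limit on infarct volume (Section 6.5), so late subjects may be selected to do better. It would be wrong to conclude that Trevo must look worse.

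Fourth, restriction to 0–16 h does not make the families comparable. Up to 16 h the device is selected on vessel anatomy (Section 6.8.3), not by randomisation. The cut is also slightly imprecise: Section 6.2 words the rule by time at randomisation but the Solitaire limit by time of use, so a subject randomised just before 16 h may still be confined to Trevo. Both points stand, and the fix takes them into account.

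**Conclusion.** The point holds as a minor one. As the protocol describes Section 8.3.5, its family analysis is confounded with treatment time by the rule in Section 6.2, and no time cut in the plan isolates 16–24 h. Under the assumed inputs, identical families would appear about 0.5–5 points apart (6.8 if Trevo is 30% of earlier Controls), in either direction. Envi-SR v Solitaire would shift by up to 3 points. If few subjects are late or outcome varies little with time, the effect is negligible; across the assumed range it is small against sampling error.

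A reader might infer that the trial's main result is at risk. It is not. The primary analysis compares the randomised arms as wholes, both enrolling over 0–24 h, and no margin, sample size or success criterion depends on 8.3.5.

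**What to change.** Add to Section 8.3.5 and to the SAP:

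- Comparisons by Control family, and of Envi-SR with each family, are made among subjects randomised within 16 h of onset or time last seen well, in both arms.
- Subjects at 16–24 h (Envi-SR v Trevo) are reported separately.
- Family is not randomised within 0–16 h, so the result is descriptive and is adjusted for the baseline stratification factors, including site of occlusion.
- Any subject whose time of device use passes 16 h after randomisation before 16 h is identified, so that the boundary is handled consistently.

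The cost is a few sentences and slightly fewer subjects in this one sensitivity analysis: about 5–20% of Controls under the assumed range, with a similar share of Envi-SR subjects. Time last seen well is already needed for Section 8.3.7. The primary analysis and the rules on device use do not change.
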